## **D. Description, Risks, and Justification of Procedures and Data Collection Tools.**

### **Risks to Human Subjects**

#### **a. Human Subjects: Involvement, Characteristics, and Design**

A purposive sample of patient-nurse dyads will be enrolled in this study. Participants in this study are patients with serious illness (heart failure or end-stage renal disease) and their acute care nurses. We expect to enroll 80 patients with serious illness (40 for the intervention group and 40 for the usual care control group) and 80

nurses who are directly involved in the care of the patient. The research team members will enroll all participants after each of them voluntarily decide to become a participant.

*Patients.* Each patient participant will engage in two audio-recorded interviews. For the first interview, through a narrative analysis framework, the patients will answer open-ended questions related to their illness experiences and how their illness has impacted their emotions, relationships and spirituality. This interview will last approximately 60-90 minutes. For the second interview, the patient will answer exit interview questions about their experience with the narrative intervention. This interview will last approximately 30 minutes. For the first patient interviews, the location will include their private inpatient room or private conference room in the facility. If the patient is discharged prior to the second exit interview, the exit interview may take place over the telephone.

*Nurses.* The nurses will be interviewed once. This interview will collect exit interview data related to the narrative intervention. The participant and nurse will be interviewed at separate times. For the nurse interview, the PI will coordinate a convenient time and private place to conduct the interview, which might include nurse's office, private conference in the facility, or take place on the telephone. In addition, the PI will collect the nurse's system usability scale responses during the exit interview for the usability testing.

*Patients:* For both randomized (narrative intervention) and control (usual care) groups, the involvement of patients includes participation in pre- and post-intervention data collection activities.

Intervention group: Data collection activities for patients include completing demographic and outcomes measures at baseline (enrollment). Then, they will have outcome measures collected immediately after narrative upload into the EHR (approximately 24 hours after narrative is collected), and 24-48 hours post narrative upload into the EHR. For the narrative intervention group, a one-time audio recorded interview (60-90 minutes) with the research team member will occur once baseline measures have been collected. In addition, the intervention participants will participate in a second audio-recorded audio exit interview (30 minutes) and will collect information on acceptability and feasibility of intervention. This interview will be collected in the private location of the patient's hospital room or may be collected and recorded over the telephone if patient has been discharged from the hospital.

Usual care group: Data collection activities for these patients include completing demographic and outcomes measures only at baseline (at enrollment), and again 24-48 hours after enrollment.

*Outcome Measures:* The estimated time for completion of the 64 items on the questionnaires is approximately 30 minutes. The following questionnaires are included as the outcome measures: Quality of Communication (QOC) which consists of 19 items; PROMIS-29 Profile v.2.1 of 29 items each; and PROMIS Psychosocial Illness Impact {Negative and Positive} Short-Form 8a which consist of 16 items.

*Nurses:* Data collection activities for the nurse participants will include completing a 30 minute exit interview via an audio recorded interview. For the usability testing, data collection will include testing of the EHR interface with the bedside nurses and completion of a short questionnaire at the end of the 30 minute exit interview.

Data collection activities for intervention patient participants include:

1. Completing baseline outcomes measures and demographic information, approximately 30 minutes
2. Completing the narrative intervention via a 60-90-minute audio-recorded interview
3. Completing outcome measures after narrative upload
4. Completing outcome measures 24-48 hours after narrative upload
5. Completing an exit interview via a 30-minute audio-recorded interview.

Data collection activities for the nurse participants will include completing a 30-minute exit interview via an audio-recorded interview. For the usability testing, data collection will include testing of the EHR interface with the bedside nurses and completion of a short questionnaire at the end of the 30-minute exit interview.

The participants will be recruited through the University of Colorado Hospital.

b. *Sources of Materials*

*Qualitative Data.* For this proposed project, data will only be collected by the research team. Materials include audio recordings of interviews, field notes, and correspondence (i.e., memos, emails) with research

Instructions – How to complete the COMIRB protocol template (Social)

CF-184, Effective 4-26-2010

team members. A total of 240 audio-recorded interviews will be collected—80 interviews for the narrative intervention, 80 for the patient exit interviews, 80 for the nurse exit interviews.

**Quantitative Data.** All patients (intervention and usual care group) will complete a questionnaire at baseline, immediately post narrative upload in the EHR, and 24-48 hours post narrative upload. All survey data will be captured using electronic surveys through REDCap on password-protected iPads/laptops. After each participant's baseline data is collected by the professional research assistant, the participant will be randomized to be included in either the narrative intervention or usual care group. This randomization will occur with the randomization computer-generated algorithm. After the participant is randomized, a unique study identifier for all enrolled participants will be created for a de-identified data set.

Steps of de-identification:

1. The research team will assign the patient participant a de-identified code (i.e. P1) after consent is signed. This code will be the identifier throughout the study to link the narrative interview, the REDcap surveys, and the exit interview.
2. The research team will assign the nurse participant a de-identified code (i.e. N1) that corresponds numerically with the patient participant code.
3. For the REDCap survey data:
  - a. When each participant is added to the REDcap database, the research team will add this assigned de-identified code as the participant identifier.
  - b. Since the participant needs to take the survey three times, at the time of adding the de-identified code, the exact number of times they should take the survey will be added.

c. **Potential Risks**

There are minimal risks to participants who elect to participate in these studies.

**Physical.** Participants could become fatigued during the 60-90 minutes narrative interview process; the 30 minute exit interview process and/or outcome measures data collection procedures. In this event, the research team member will encourage rest periods or, if necessary, reschedule a return visit to complete the interview. For the burden of time, each patient participant will receive \$25 in appreciation for completing the narrative intervention and then another \$25 at the time of the exit interview. For the burden of time, each nurse participant will receive \$25 in appreciation for completing the study.

**Psychological.** For the patient participants, there is minor/moderate/severe risk for psychological distress due to the sensitive topics of serious illness. We will assure that participants understand both orally and in writing that they are free to decline participation in any and all study activities at any time, including declining to answer specific questions, refusing participation in the intervention, requests to speak off the record, or complete withdrawal from the study. If any of the interview or psychometric assessment data reveal increased participant distress, dissatisfaction or any adverse event, the data collection will cease. If the participant exhibits any verbal or non-verbal distress, the research team member will allow the participant to stop the interview, reschedule for return visit to complete interview, or allow participant to withdraw consent. If moderate distress is exhibited, the research team member will assist in referring participant to emotional support either through family, friends, or the healthcare team for follow-up related to the participant's distress. If severe distress, such as noting suicidal ideation, the research team member will immediately refer patient for further work-up and care. The research team member will carry a list of contact phone numbers for such referrals. If any moderate or severe distress is noted, this will be reported immediately to the PI for help in determining if the event meets criteria for a reportable adverse event. If deemed serious adverse event, the IRB will be notified and the participant's involvement in the research study will be discontinued. Patient or nurse participants will be able to contact the PI to discuss any concerns or questions at any time during their participation in the study. In a previous study using this methodology, none of these adverse events occurred. Therefore, we anticipate these risks to be rare events given the nature of the data collection procedures.

*Social.* One primary concern is the possible perception of coercion due to participant recruitment in health care settings. We will attempt to avoid perception of coercion by emphasizing the voluntary nature of participation and the ability of the participants (patient or nurse) to withdraw at any time without penalty. Participants could feel pressured to participate in the proposed project. The research team members will arrange with the participants a private location with only research team member and participant present for collection of the interview. Once in this private setting, the research team member will remind them that participation is voluntary and that they may withdraw from the project at any time without any penalty or prejudice.

*Breach of confidentiality.* Safeguards for protecting anonymity of participants will include creating a master list of names with corresponding numbers assigned to participants at the time of the screening by the PI. Once assigned, the corresponding numbers will then be used to de-identify the remainder of participants' personal information and each participant's interview transcript. Only de-identified transcripts of interviews will be available for the remainder of the research team for analysis and interpretation processes.

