## III. Preliminary Studies/Progress Report

### Relevance of Research to My Career Goals

I have based my research program on the ORBIT model for developing and testing behavioral intervention ( Figure 1). During my dissertation, I conducted qualitative work that provided a rich understanding of how to form a significant clinical question: How can narrative interventions be used to improve communication among patients with serious illness and their providers? Using this question, my K99 study assisted in refining and defining the narrative intervention (Phase 1). For this R00 proposal, preliminary testing of the narrative intervention will be studied (Phase II).

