*Nurse recruitment.* After a patient is enrolled, the research team will collect from the EHR the names of the nurses who cared for the enrolled patients. These nurses will be approached for consent to participate in the study, with the goal of 80 participating nurses for collection of exit interviews. For the nurses who patients were randomized to the intervention, additionally, these 40 nurses will complete the user-centered testing which consists of nurse participant completion of the system usability scale questionnaire and providing any feedback to PI on ease of use, relevance and appeal, efficiency and subjective satisfaction of the nurse’s use of the patient’s story. Nurses will be contacted via e-mail or in-person with a recruitment flyer. After receiving verbal consent for participation via e-mail or in-person, a convenient in-person time will be coordinated for obtaining consent and subsequent data collection for the exit interviews and/or user centered testing. Each nurse will receive \$25 after completing the exit interview.

Weekly follow-up e-mails x 3 times will be sent if there are difficulties recruiting the 80 nurses for exit interviews or the 40 nurses for user-centered testing. If after these three e-mails, the nurse does not enroll, then the research team will attempt to recruit another nurse who attended the patient. Patient participants will not be withdrawn from the study even if a patient participant’s nurse is not enrolled.

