### Aim 2: Process Measures:

**Barriers and facilitators.** The patient and nurse will be contacted for exit interviews. These will be collected 5-7 days after the meta-narrative is added to the EHR. The transcribed exit interviews will be entered into ATLAS.ti, and an interpretive approach will inform the understanding of the patients' and nurses' perspectives related to barriers and facilitators. Open coding, which allows codes to form patterns as they emerge from the transcripts, will be used for the thematic analysis. An inductive approach to coding, through the use of the participant's actual words, will be used for up to three transcripts. Once the initial codes are chosen, the transcripts will be read again through an iterative process defined as "a movement back and forth through" data coding for creating thematic analyses.71(p86) As PI, I will complete the preliminary coding for each transcript then the research team will review my preliminary codes. Once the first three transcripts are coded, the research team will analyze the preliminary codes across the remainder of the transcripts. Throughout the entire analytical process, the codes will be refined. At each of the monthly research team meetings, codes can be expanded or collapsed as part of the iterative process. To ensure the rigor of the data analysis, Sandelowski's criteria for trustworthiness will be used.

**Usability testing.** Following the exit interview, the nurse participants will be asked to complete the System Usability Scale (SUS), which asks them to rank their experience and satisfaction with specific elements. Usability is defined as the relationship between humans and computers. Usability testing focuses on evaluating Instructions – How to complete the COMIRB protocol template (Social)

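### The nurses' usability scale is collected by the intervention's developer during or after an interview about that intervention; private completion beforehand would be a cheap improvement

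*Combined protocol and SAP*

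**What the plan says.** The combined protocol and SAP describes collection of the SUS in several places.

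- Section IV.D, Human Subjects, Nurses: "the PI will collect the nurse's system usability scale responses during the exit interview". The same paragraph says of the interview: "This interview will collect exit interview data related to the narrative intervention". It allows a private place in the facility or the telephone.
- Section IV.D, the two near-identical paragraphs on nurses' data collection: "completion of a short questionnaire at the end of the 30 minute exit interview". No collector is named.
- Section IV.F, Aim 2, Usability testing: "Following the exit interview, the nurse participants will be asked to complete the System Usability Scale (SUS"). No collector is named here either.
- Section IV.C, Nurse recruitment: the 40 nurses whose patients were randomized to the intervention complete the SUS. Their user-centered testing also includes "providing any feedback to PI on ease of use, relevance and appeal, efficiency and subjective satisfaction". An in-person session is planned.

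The PI is the developer. Writing in the first person, section III says that "my K99 study assisted in refining and defining the narrative intervention".

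Table 1 lists the SUS (10 items) as the nurses' only questionnaire. Aim 2 also names analysis of EHR interface use as a source on usability, and section IV.F lists observation of nurses and chart or log analysis.

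**The concern.** A respondent who gives ratings of a tool to the person who made it may be kinder than one who answers in private. A respondent who has just spent up to 30 minutes talking about the tool may also rate the conversation as much as the tool. Both effects can be avoided by changing the order and manner of collection.

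The design gives no internal protection. Only intervention-arm nurses complete the SUS, so there is no second group in which a common favourable shift would subtract out. Aim 2 is meant to establish usability, and the results are to inform an R01 efficacy trial. If the score is raised, some barriers to using the narrative in the EHR may look smaller than they are. Section III already reports that all eighteen K99 nurses had positive experiences. That may be wholly genuine, but further favourable ratings add more when they are collected in a way that makes criticism easy.

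**Working it through.** The plan states no SUS target, SD, test or precision, so there is no figure to reproduce. The check is mainly a comparison of the text.

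**1. Timing and collector.**

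| Place | Timing of SUS | Collector named |
|---|---|---|
| IV.D, Nurses | during the interview | PI |
| IV.D, nurses' data collection (two paragraphs) | at the end of the interview | none |
| IV.F, Usability testing | after the interview | none |

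The three timings differ and need reconciling in any case. None puts the SUS before the interview.

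**2. Safeguards.** Three were looked for: completion before the interview, private completion, and a collector other than the PI. None is stated. Survey data are captured in REDCap on iPads or laptops (IV.C, Data collection; IV.D, Sources of Materials). This fixes the medium but not who is present. Nurse codes match patient codes by number, and the master list is kept in the PI's office, so answers are coded but not anonymous.

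**3. No cancelling.** Let μ be the mean rating under private completion and b the average shift from courtesy or priming. The single-group mean estimates μ + b. More nurses narrow the interval around μ + b and do not reduce b.

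**4. Illustration of size.** From the documents: n = 40 nurses (IV.C) and 10 items (Table 1). Assumed: a 0–100 score from ten equally weighted five-category items, so one category on one item is 100 / (10 × 4) = 2.5 points; SD of 10 to 25 points; b of 3, 5 or 10 points. A shift of 5 points is 5 / (10 × 2.5) = 0.2 of a category per item.

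- SE = SD / √40
- 95% half-width = t(0.975; 39 df) × SE, with t = 2.02
- Coverage of μ = Φ(1.96 − b/SE) − Φ(−1.96 − b/SE)

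| SD | SE | Half-width | Coverage, b = 3 | b = 5 | b = 10 |
|---|---|---|---|---|---|
| 10 | 1.58 | 3.2 | 0.525 | 0.115 | 0.000 |
| 15 | 2.37 | 4.8 | 0.756 | 0.441 | 0.012 |
| 20 | 3.16 | 6.4 | 0.842 | 0.647 | 0.115 |
| 25 | 3.95 | 8.0 | 0.882 | 0.756 | 0.284 |

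Example, SD 15 and b = 5: b/SE = 5 / 2.37 = 2.11, and Φ(−0.15) − Φ(−4.07) ≈ 0.44.

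The table shows what a shift of a given size would do. It is not evidence that a shift occurs.

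**The case against.** The strongest reply is that the stakes are low and the plan has other sources. The SUS carries no threshold, test or stated go/no-go role. Aim 2 also draws on observation of nurses and on chart or log analysis, and log data do not depend on what a nurse tells the PI. The interviews themselves ask for barriers. All of this stands, and it is why the point is minor.

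Self-entry in REDCap may already be intended, since section IV.F has nurses complete the scale themselves. That is possible, but section IV.D still has the PI collecting it during the interview, and privacy is nowhere stated.

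Completing the SUS first could prime the interview. This is a fair but small cost: ten general items are less likely to steer an open interview than a long discussion is to colour a rating.

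A reader might infer several stronger points that the documents do not support:

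- *One person fills every nurse-facing role in Aim 2.* The PI is named for SUS collection and first coding, but the section on recruitment and informed consent makes research team members responsible for collecting interviews.
- *The rating is always given face to face.* The telephone is allowed.
- *The SUS is the only quantitative usability evidence.* It is the only named rating scale. Log analysis could also be numeric, and the list of measures in section IV.F is cut off in the text available.
- *First coding by the PI is a defect.* Section IV.F says "I will complete the preliminary coding for each transcript then the research team will review my preliminary codes", followed by revision at monthly team meetings and named trustworthiness criteria. Independent double coding would be a methodological preference.

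**Conclusion.** A cheap improvement of minor severity. As written, the only named usability rating scale is taken during or after an interview about the intervention. Section IV.D has its developer collect it, in person or by telephone, with no stated safeguard and no comparison group. That leaves the score open to courtesy and priming bias, and the three descriptions of timing disagree.

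A reader might go further and conclude that the score will be inflated, or that an inflated score could never be told from a usable tool. Neither follows. The documents do not show that a shift occurs, its size is unknown, and the planned observation and log analysis offer a partial check. The 44% to 65% coverage at SDs of 15 to 20 rests wholly on the assumed scoring, SD and 5-point shift. The primary Quality of Communication outcome and the patient-reported secondary outcomes are not affected.

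**What to change.** Use one statement in the four places that describe SUS collection: the Nurses paragraph and the two data-collection paragraphs of section IV.D, and Usability testing in section IV.F. It should say that the nurse completes the SUS alone in REDCap, immediately before the exit interview, and that the PI does not see the answers until that interview is finished. This settles the timing, removes priming by the interview, and takes the developer out of the moment of rating. It does not make the answers anonymous and should not be described as doing so.

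The cost is one REDCap survey link and wording in four places, with no extra staff or visit. There are two downsides: an occasional item may be left unclear with nobody present to explain it, and the SUS items may slightly prime the interview. The change should be made before nurse data collection starts, because ratings already taken in the other order cannot be corrected afterwards. No change to the coding procedure is asked for.

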**Figure 2. Narrative Intervention Flow Diagram**

**Narrative Intervention group.** The intervention in this study is a co-created narrative whereby patients share their illness narrative with a research team member through an open-ended, audio-recorded interview about their illness. During the interview, patients are prompted to share their narrative through probing questions or statements such as: tell me about your illness; tell me how your illness has affected your emotions, your relationships, and your spirituality. These probing questions have been field tested during my dissertation research and K99 study. As the patient responds, the research team member takes field notes and audio-records the interview.

The audio-recorded interview is then transcribed verbatim, and the research team member will create a one- to two-page meta-narrative. Criteria are that the patient’s narrative is: 1) written in the patient’s first-person voice; 2) nonjudgmental; 3) captures the patient’s voice; 4) accurately reflects the content of the interview; 5) is Instructions – How to complete the COMIRB protocol template (Social) CF-184, Effective 4-26-2010

non-diagnostic (not labeling). The co-created patient narrative is then returned to the patient within 48 hours, and the patient reads his/her written narrative. At that member checking follow-up session, the patient is encouraged to make any desired changes, which facilitates co-creation of the patient's narrative. Once the narrative is approved by the patient, the patient's narrative will be uploaded to the EHR. Once the narrative is uploaded into the EHR, the assigned nurse will be alerted that the patient's narrative is ready to be read. The workflow diagram is depicted in Fig 2.

**Usual care group.** The intervention group will be compared to a usual care group of participants: hospitalized patients who meet the same eligibility criteria as the narrative intervention group. Because there are few interventions in place to increase communication among patients and nurses, the use of a usual care patient group is the most appropriate comparison.

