## F. Data Analysis Plan.

**Aim 1 Analysis Plan.** Statistical analyses will be performed with the use of SAS software, version 9.4. In preliminary analyses, data will be screened for errors and outliers; appropriate transformations will be made for non-normal outcomes. Baseline demographics will be summarized using standard descriptive statistics. The pattern of participant dropout will be examined to ensure a reasonable equal distribution of participants lost to follow-up between groups and based on baseline characteristics. Maximum likelihood techniques will include participants with incomplete data without need for imputation. In addition, we will conduct sensitivity analyses to examine the effect of departures from key assumptions made in the main analysis and to help determine effects of missing data. Using an intent-to-treat approach, primary and secondary outcomes will be analyzed with linear mixed models using SAS Proc Mixed to compare the two groups (narrative intervention versus usual care) over the assessment period. Separate models will be estimated for each of the primary and secondary outcomes, though relationships among outcomes will also be assessed. Mixed models will specify intervention group and time as fixed effects and subject as a random effect. Pairwise comparisons testing group effects at each time point are proposed to disentangle the effects of intervention process versus change in quality of communication between patient and nurse. All statistical analyses will be done in consultation with the project statistician, [name].

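### Intervention-arm follow-up is timed from narrative upload, and no Time 2 or Time 3 date is given for a randomised patient whose narrative is never uploaded

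*Combined protocol and SAP*

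**What the plan says.** All references are to the combined protocol and SAP.

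- **Intervention-arm timing (IV.D, part a, Intervention group).** After baseline, patients have "outcome measures collected immediately after narrative upload into the EHR (approximately 24 hours after narrative is collected), and 24-48 hours post narrative upload". The numbered list of intervention-patient activities repeats the anchor: item 3 is "Completing outcome measures after narrative upload" and item 4 is "Completing outcome measures 24-48 hours after narrative upload".
- **Usual-care timing (same part).** These patients are measured at enrolment "and again 24-48 hours after enrollment". No second follow-up is listed.
- **Sources of Materials (IV.D, part b).** "All patients (intervention and usual care group) will complete a questionnaire at baseline, immediately post narrative upload in the EHR", with a third questionnaire 24-48 hours after upload. Randomisation follows the baseline questionnaire. The de-identification steps here, repeated under Confidentiality, have each participant take the survey three times.
- **Table 1 (IV.A).** Time 2 is 24-48 hours after baseline or narrative upload, the two joined by an unexplained slash. Time 3 is counted from Time 2.
- **Measures (IV.C).** Outcomes are to be collected from all patients at three time points, with consistent timing across arms as the stated purpose.
- **Condition for upload (IV.C, Narrative Intervention group).** The draft goes back to the patient within 48 hours, and it is uploaded "Once the narrative is approved by the patient".
- **Right to decline (IV.D, part c, Psychological).** Patients may decline study activities, including "refusing participation in the intervention, requests to speak off the record, or complete withdrawal from the study".
- **Analysis (IV.F).** "Using an intent-to-treat approach, primary and secondary outcomes will be analyzed with linear mixed models". Maximum likelihood is to handle incomplete data. Section IV.E also states intention to treat.

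**The concern.** The right to decline lists refusal of the intervention separately from complete withdrawal. The protocol therefore foresees a patient who is randomised to the narrative, stays enrolled and never has an upload. The same can happen if the interview is not finished or the patient does not approve the text. All of these events come after randomisation, and only the intervention arm has them.

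Section IV.D times both intervention-arm follow-ups from the upload. Staff who follow that section have no date on which to survey such a patient. Whether outcome data exist would then depend on completing the assigned intervention.

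Patients who find the narrative too hard may plausibly differ on anxiety, depression, illness impact and perceived communication, which are the outcomes. The sample size section says the trial should supply outcome means and standard deviations for the planned efficacy trial, so a selected intervention mean would carry over into that trial's planning.

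**Working it through.** **1. Is there a date for a patient without an upload?**

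| Place | Time 2 anchor | Time 3 anchor | Date if no upload? |
|---|---|---|---|
| IV.D part a, intervention text and list items 3-4 | Upload | Upload | No |
| IV.D part b, Sources of Materials | Upload, both arms | Upload, both arms | No |
| Table 1 | Baseline or upload (slash) | Time 2 | Only if the slash allows baseline in this arm |
| IV.C Measures | None; refers to Table 1 | None; refers to Table 1 | No |
| IV.D part a, usual care | Enrolment | Not listed | Not applicable |

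The slash in Table 1 may mean one clock per arm or a choice within an arm. Under the first reading Time 2 is undefined without an upload, and so is Time 3, which is chained to it.

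**2. The plan's own power figure.** Section IV.C states 80% power with N = 80 at f = 0.14, and f = 0.16 after 20% attrition (N = 64). For a group-by-time interaction with k = 2 groups and m = 3 times, I used the noncentral F with λ = f²·N·m/(1−ρ), df1 = (k−1)(m−1) and df2 = (N−k)(m−1). The plan does not state ρ; 0.5 with sphericity is assumed.

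- N = 80: λ = 0.0196 × 240 / 0.5 = 9.41, df 2 and 156, power 0.782.
- N = 64: λ = 0.0256 × 192 / 0.5 = 9.83, df 2 and 124, power 0.798.

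Both agree with the plan to within 2 points. For ρ from 0.3 to 0.7 the first figure runs from 0.627 to 0.949.

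**3. Power if patients without an upload go unmeasured.** Let u be the share of the 40 intervention patients with no upload. It is not in the documents. Effective N = 4·n₁·40/(n₁+40), with n₁ = 40(1−u).

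- u = 10%: n₁ = 36, effective N = 75.8, power at f = 0.14 is 0.757.
- u = 20%: n₁ = 32, effective N = 71.1, power 0.728.

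The power loss is modest.

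**4. Shift in the observed-case mean.** Let patients without an upload score δ SD worse than the others, whose mean is μ. The mean of the whole arm is (1−u)μ + u(μ−δ) = μ − uδ, so the measured patients overstate it by uδ. Both inputs are assumed.

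| | δ = 0.5 | δ = 0.8 |
|---|---|---|
| u = 10% (4 of 40) | 0.05 | 0.08 |
| u = 20% (8 of 40) | 0.10 | 0.16 |

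Against the stated d = 0.28, 0.05/0.28 = 18% and 0.16/0.28 = 57%. A wider range, u = 5-30% and δ = 0.25-1.0, gives 0.01 to 0.30 SD.

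**5. What the K99 result allows.** All 20 patients completed data collection. The exact upper limits for 0 of 20 are 1 − 0.05^(1/20) = 13.9% (one-sided 95%) and 1 − 0.025^(1/20) = 16.8% (two-sided 95%). Of 40 patients these are 5.6 and 6.7. The K99 figure counts completed data collection, not refusal or non-approval of a narrative, so it is only a rough guide to u.

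**The case against.** A reader might infer that patients without an upload get no follow-up visit, that intention to treat is therefore broken, and that the trial compares narrative completers with all controls. The documents do not support this.

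- **No visit is omitted by rule.** The Measures paragraph and the de-identification steps call for three surveys from everyone, with the number entered in REDCap when the participant's code is added, not at upload. Table 1 can be read as allowing a baseline clock. No section excludes these patients. The date is undefined; the visit is not cancelled.
- **The control arm is not complete either.** Section IV.D lists one follow-up for usual care, so on that text Time 3 has no controls.
- **Intention to treat is not abandoned.** Patients stay in their randomised arm and maximum likelihood keeps their baseline data. Section IV.F also plans a check of dropout by group and baseline characteristics, and sensitivity analyses for missing data.
- **Stopping need not mean no upload.** Interviews may be rescheduled, and the patient may edit the draft before upload.
- **The size is assumed.** No K99 patient reported the intervention as too burdensome, and the 0.05-0.16 SD is not the bias of the planned mixed model.

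All of this stands against the stronger reading. It does not supply the missing date. A patient without either follow-up contributes only baseline scores, so maximum likelihood helps only as far as those scores predict who has no upload. The sensitivity analyses are not specified. An intention to measure everyone favours stating how it will be done.

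**Conclusion.** The point holds as a gap in the follow-up schedule that puts the intention-to-treat comparison at risk; it does not show that the comparison is broken. The risk arises if staff follow the upload trigger in section IV.D as written: missing follow-up in the intervention arm would then depend on uptake.

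The size is unknown. The 0.05-0.16 SD rests on an assumed 10-20% without upload and an assumed gap of 0.5-0.8 SD in the unfavourable direction. It describes observed cases before any recovery through baseline scores. If uptake is as complete as K99 data collection was, the effect is nil. Selection is the concern more than power. The gap is worth closing because the remedy is cheap and the trial is meant to inform a later one.

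**What to change.** Reconcile Table 1, the Measures paragraph in IV.C, and parts a and b of IV.D, so that they say:

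1. Every randomised patient who has not withdrawn from data collection completes both Time 2 and Time 3, whatever the upload status.
2. For an intervention patient without an upload, both visits follow the Table 1 schedule counted from baseline: Time 2 from baseline, Time 3 from Time 2. The usual-care text in IV.D cannot serve as this clock, because it has no Time 3.
3. A window is allowed where non-approval is known late. The draft may come back up to 48 hours after the interview, by which time a visit due 24-48 hours after baseline may have passed.
4. The reason for no upload is recorded in REDCap.
5. These patients are analysed in their randomised arm.
6. Declining or not finishing the narrative is not in itself withdrawal from outcome collection.

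The distress and safety rules under Potential Risks and Protections Against Risk stay unchanged. Patients whose data collection ends under those rules would still be missing.

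The cost is protocol wording and one REDCap field; the surveys, staff and devices are already planned. The downside is a few extra surveys, which patients may decline, and slightly variable timing for this group.
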